3.2.1 Primary Outcome Measures

The primary endpoint is progression of disease at 2 years (POD24).

POD24 will be analyzed according to the survival analysis methods. The quartiles with their 95% confidence interval (estimated using Kaplan-Meier methods and Greenwood's formula) will be presented. Kaplan-Meier plots with a 95% CI will be prepared. Estimates for the survivor function will be obtained by the Kaplan-Meier approach.

Moreover, the POD24 will be analyzed as binary variable. Number and percentage of patients with its 95% CI for POD24 will be calculated.

Logistic regression analysis will be performed to assess which variables are predictive of POD24. To identify factors associated with POD24, logistic regression analysis will be performed with backwards selection (removing factors with $P > 0.05$). Univariable associations between factors and POD24 will be calculated by using the Chi-square test.

In the analysis of POD24 will be excluded patients who die within 24 months from the treatment start with Obinutuzumab for reasons not related to the disease progression.

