6.1.1 Overview of Study Design

A schedule of activities is provided in Appendix 2.

Figure 1 Study Scheme

Start Date of Study:

The study start date will be the date of the first data collection: the date from which information on the first study patient is recorded in the study database. The planned start date is July 2019.

End of Study:

The end of the study will be the date from which the last information of the last patient *still in the study* is recorded in the study database. The planned end date is December 2024.

The overall length of the study will be approximately 5 years.

This study will last 66 months. This period includes approximately 24 months of recruitment and 42 months after the last patient has started treatment with Obinutuzumab.

In addition, the Sponsor may decide to terminate the study at any time.

A data collection overview is provided in Appendix 2.

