1.2.1 Effectiveness Objectives

The primary effectiveness objective of this study is as follows:

- 1) To evaluate the effectiveness of Obinutuzumab in combination with chemotherapy in previously untreated advanced follicular lymphoma (FL) patients, in the real world setting as measured by the proportion of patients relapsed within 24 months from start of therapy (POD24).

The secondary effectiveness objectives of this study are as follows:

- 2) To evaluate the progression free survival (PFS) at 2 and 3 years;
- 3) To evaluate the overall and complete response rates at mid and end of induction, and during and after maintenance therapy (including the complete response rate at 30 months [CR30]), as per clinical practice, with and without 18F-fluorodeoxyglucose – positron emission tomography (FDG-PET);
- 4) To describe patient/disease characteristics and the second line regimens prescribed for patients who progressed after first line therapy during the overall study duration and within 24 months from start of therapy (POD24);
- 5) To explore the effectiveness of Obinutuzumab in different patient subgroups, stratified by follicular lymphoma International Prognostic Index (FLIPI) – intermediate and high, ECOG performance status (PS), age at study entry, chemotherapy backbone choice, hepatitis infection (history of past/resolved infection or latent HBV after prophylaxis as per standard treatment guidelines), presence of autoimmune disease, history of renal failure and liver failure.

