3.1 ANALYSIS POPULATIONS

The following populations will be considered for data analysis:

Effectiveness population

Effectiveness analysis population includes all patients who are enrolled and have received at least two cycles of Obinutuzumab.

Safety population

Safety analysis population includes all patients who are enrolled.

Screening failures are not considered for the analyses.

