3.2 EFFECTIVENESS ANALYSIS

Effectiveness analysis population includes all patients who are enrolled and have received at least two cycles of Obinutuzumab.

In general, the time to endpoint will be defined as an interval between the date of enrolment (date of first visit) and date of first occurrence of the event. For patients who are event free, the censoring time will be calculated as a time interval between date of enrolment and the patient's final contact with available data concerning the event. The estimates and graphical presentation will be performed via Kaplan-Meier approach.

Logistic regression will be performed on the rate of endpoints in order to test the impact of covariates, i.e. age, sex, ECOG PS, Ann Arbor staging, FLIPI, hepatitis infection

(history of past/ resolved infection or latent HBV after prophylaxis as per standard treatment guidelines), chemotherapy backbone choice, medical history and history of FL, comorbidities.

Exploratory analysis between different medical treatments given or subgroup analysis will be performed using Cox regression model and including relevant covariates.

Corresponding 95% confidence intervals (CIs) will be provided for all statistical estimates.

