3.8 INTERIM, FINAL ANALYSES AND TIMING OF ANALYSES

An interim analysis will be performed approximately one year after the first patient is included in the study in order to evaluate safety data (particularly, infections and events COVID related), demographic data (including potentially differences in patient enrolled pre- or post- COVID19 pandemic), FLIPI, treatment choices (obinutuzumab prescription profile and chemotherapy backbone choice per Italian region, per age range, per patient's profile and site dimension - outlying sites/ universities, etc.), impact of COVID19 over maintenance delay and treatment adherence.

A second interim analysis will be performed approximately two years after the first patient included in the study in order to evaluate safety and primary, and secondary effectiveness data (including POD24), and the impact of COVID-19 on the patients management.. Tables template for second interim analysis is reported in Appendix 3.

The final analysis will be performed at the end of the study.

4. **REFERENCES**

Armitage JO. Treatment of non-Hodgkin lymphoma. *N Engl J Med* 1993; 328(14):1023-30.

Cartron G, de Guibert S, Dilhuydy MS, et al. Obinutuzumab (GA101) in relapsed/refractory chronic lymphocytic leukemia: final data from the phase 1/2 GAUGUIN study. *Blood* 2014;124:2196–202.

Izutsu K. Treatment of follicular lymphoma. *J Clin Exp Hematop* 2014;54(1):31-7.

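### The binary POD24 percentage has no rule for event-free patients observed under 24 months, and the 24-month Kaplan-Meier value is not named as the POD24 rate, so the second-interim percentage would be biased under either natural reading

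*SAP*

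**What the plan says.** The primary objective in SAP 1.2.1 is a proportion: "as measured by the proportion of patients relapsed within 24 months from start of therapy (POD24". SAP 2.3 and protocol 6.3.1 define POD24 as a time from treatment initiation, with a censoring rule for patients without an event.

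SAP 3.2.1 and protocol 6.7.1 analyse it in two ways:

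- **Time to event.** Quartiles with 95% CIs, plots, and "Estimates for the survivor function will be obtained by the Kaplan-Meier approach". SAP 3.2 adds 95% CIs for all estimates. No 24-month value is named.
- **Binary.** "Moreover, the POD24 will be analyzed as binary variable. Number and percentage of patients with its 95% CI for POD24 will be calculated". The sample size in SAP 2.6 and protocol 6.7.5 is justified on this version.

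The only population defined for effectiveness is in SAP 3.1: "Effectiveness analysis population includes all patients who are enrolled and have received at least two cycles of Obinutuzumab". The only stated exclusion is in SAP 3.2.1: "In the analysis of POD24 will be excluded patients who die within 24 months from the treatment start with Obinutuzumab for reasons not related" to progression. SAP 3.6 says missing data are not imputed, and SAP 3.4 plans no sensitivity analyses.

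On timing, SAP 3.8 places the second interim "approximately two years after the first patient included in the study in order to evaluate safety and primary, and secondary effectiveness data (including POD24"). Protocol 6.1.1 says of the study duration: "This period includes approximately 24 months of recruitment". SAP 2.1 admits patients after at least two cycles and within one year of starting treatment.

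On the time origin, SAP 3.2 states: "In general, the time to endpoint will be defined as an interval between the date of enrolment (date of first visit"). Protocol 6.7.1 says the same.

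**The concern.** The censoring rule deals with short follow-up in the time-to-event version. The binary version has no counterpart, although it is the one used to justify the sample size. Two readings come naturally. One keeps the whole effectiveness population (less other-cause deaths) in the denominator, so a patient seen for ten months without progression counts as a non-event. The other drops patients whose 24-month status is unknown but keeps every early progressor. The first errs low and the second errs high.

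This matters most at the second interim, where POD24 is to be reported while recruitment is only just ending. The study is descriptive, so no test decision is at risk. What is at stake is an interim rate for the primary endpoint that could mislead, with an interval that does not show it. The planned Kaplan-Meier fit handles incomplete follow-up, but the summary named first, quartiles, would probably not be reached at the rates the plan expects.

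**Working it through.** **1. The plan's own figure.** Exact Clopper-Pearson limits for 39/300 (13%) are 9.41% to 17.34%, width 7.93 points. The plan states 9.4 to 17.3, width 7.9. It reproduces.

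**2. Quartiles do not give the rate.** Under a constant hazard the first quartile is 24 × ln(0.75)/ln(1 − p): 59.2, 49.6, 42.5 and 37.1 months for p = 11, 13, 15 and 17%, all beyond the 24-month window.

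**3. Inputs for the interim.** From the documents: p = 13%, n = 300, 24 months of recruitment, a cut at about 24 months, and enrolment no later than 12 months after treatment start. Assumed: uniform accrual, constant hazard, lag uniform on 2-12 months (extremes: every lag 2 or every lag 12), enrolment not affected by early progression, no other-cause deaths. A 30-month cut is shown as well. The planned start was July 2019 and the SAP's signature certificate is dated early 2022, which is about 30 months; the date of first inclusion is not given.

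**4. Share with 24 months observed.** Follow-up from treatment start is cut − U(0,24) + lag, so the share is M = (cut − 24 + lag)/24, with mean lag 7 in the base case.
- 24-month cut: 7/24 = 29% (2/24 = 8% to 12/24 = 50%).
- 30-month cut: 13/24 = 54% (8/24 = 33% to 18/24 = 75%).

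**5. All patients in the denominator.** With λ = −ln(0.87)/24 = 0.00580 and F(t) = 1 − exp(−λ·min(t,24)), the expected percentage E is the mean of F over follow-up. Example with every lag 12 and a 24-month cut: half the patients contribute 13.000%; the other half, followed for 12-24 months, contribute 9.899% on average; E = (13.000 + 9.899)/2 = 11.4%.

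**6. Unknown status dropped.** The percentage is E/(E + 0.87·M). Base case: 0.0976/(0.0976 + 0.87 × 0.2917) = 0.0976/0.3514 = 28%.

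**7. Coverage under the all-patients reading.** This is an exact binomial sum with n = 300, using the SAP's own interval (Poisson below 10%, Clopper-Pearson otherwise; SAP 3).

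| Cut | All patients | Unknown dropped | Coverage of 13% (all patients) |
|---|---|---|---|
| 24 months | 9.8% (7.7-11.4) | 28% (21-51) | 70% (22-93) |
| 30 months | 11.6% (10.2-12.6) | 20% (16-26) | 94% (78-97) |

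Clopper-Pearson alone would give 63% and 91%, but about 53% of base-case interims at 24 months fall below 10%, where the SAP switches to Poisson. With Weibull shapes 0.7-1.5 and lags 1.5-12 months, the all-patients figure at a 24-month cut ranges from 6.1% to 11.9%, always below 13%.

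**8. After the fix.** Kaplan-Meier 1 − S(24) in simulated cohorts of 300 averages 13.0%. Its 95% CI width is 9.4 points (8.3-12.0) at a 24-month cut and 8.2 (7.7-9.1) at 30 months. A percentage limited to patients started at least 24 months before a 24-month cut has about 300 × 0.292 = 88 patients (25-150) and a mean Clopper-Pearson width of 14.9 points (28.5-11.3).

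**9. Final analysis.** Only loss before 24 months matters. If a share q is lost uniformly over months 2-24, mean F among those lost is 7.20%, so the all-patients percentage is 13(1 − q) + 7.20q: 12.7% at q = 5%, 12.4% at 10%, 11.8% at 20%.

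**The case against.** The strongest reply is that the plan already contains most of the remedy. POD24 is defined first as a censored time, survivor-function estimates are planned, and 95% CIs are promised for all estimates. That stands. A reader might infer that the proportion is left to the raw percentage alone; the documents do not support that. The gap is narrower: the 24-month value is not named as the reported rate.

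A reader might also infer that the SAP counts short follow-up as non-events and so would report too low a rate. It states no such rule. SAP 3.6 rules out imputation, and SAP 2.6 speaks of 300 evaluable patients without defining the term, both of which could point to a restricted denominator. The direction of the error is therefore not fixed.

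The SAP 3.8 interim tables are in Appendix 3, whose content is not visible. They may state a denominator, and their absence from the public text is not a fault in the plan.

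The enrolment origin in SAP 3.2 can look like a contradiction. It is worded as a general rule, and the specific POD24 definition in SAP 2.3 naturally governs. The two need harmonising, no more.

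Defining evaluable as 24 months since treatment start, plus a rule for loss, would also close the gap and keep the Clopper-Pearson basis. It is a fair alternative, at the cost of many interim patients.

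**Conclusion.** The concern holds as an undefined rule that affects the second interim. Under the assumptions in the working, the interim percentage is about 3 points too low (9.8% against 13%) or about 15 points too high (28%), depending on a choice the visible text does not make. At a 30-month cut the errors shrink to about 1.4 points low or 7 points high. The sizes depend on the accrual, lag and hazard assumptions. Within each reading, the direction was the same in every scenario run.

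A reader might extend this to the final analysis. The figures do not support that: under assumed loss of 5-20% the all-patients percentage is 12.7-11.8%, a shift of about 1 point or less against a planned width of 7.9 points. This should be fixed, but it does not undermine the study's main result.

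**What to change.** In SAP 3.2.1 and protocol 6.7.1:

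- Report 1 − S(24) from treatment start, with its 95% CI, from the planned Kaplan-Meier fit. Make it the POD24 rate at the second interim and show it alongside the binary percentage at the final analysis.
- Limit any interim binary percentage to patients whose treatment started at least 24 months before data cut-off.
- State how patients lost event-free before 24 months are counted in the binary percentage, and report their number.

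In SAP 3.2 and protocol 6.7.1, replace the general enrolment origin with the origin in each endpoint's definition, which for POD24 is treatment start (SAP 2.3, protocol 6.3.1). If the Appendix 3 templates already define a denominator, align them with this wording. The quartiles and the exclusion of other-cause deaths can stay.

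The cost is wording plus one time point read from a fit already planned; no new data are needed. The interim interval is no longer the Clopper-Pearson interval used for planning, and the restricted interim percentage rests on fewer patients (about 88 of 300 in the base case). At the final analysis the Kaplan-Meier width of 7.6-8.0 points (0-20% loss) looks close to the planned 7.9, but it is not like for like. The planned width uses exact limits, whereas the large-sample width with no loss is 2 × 1.96 × √(0.13 × 0.87/300) = 7.6 points.

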6.1.3 Number of Patients Observed in the Study

Approximately 300 patients will take part in this study.

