6.7.5 Determination of Sample size

Sample size of this clinical study is selected based on feasibility.

Sample size is justified for the primary effectiveness endpoint POD24 treated as binary variable.

A sample size of 300 evaluable patients will allow estimation of the two-sided 95% confidence interval with a width equal to 7.9% (precision 3.95%) of the POD24 when the expected percentage is equal to 13%.

The Clopper-Pearson's formula has been used for the computation.

Table 1 provides the actual width and the precision of the 95% CI and the 95% confidence limits for different percentages of POD24 when the sample size is equal to 300 evaluable patients.

Table 1 - POD24 rate and corresponding 95% Confidence Intervals

POD24 (%)	Actual Width (%)	Precision (%)	95% Clopper-Pearson Exact CI (%)
11%	7.4	3.70	From 7.7 to 15.1
13%	7.9	3.95	From 9.4 to 17.3
15%	8.4	4.20	From 11.2 to 19.6
17%	8.8	4.40	From 12.9 to 21.7

Moreover, a sample size of 300 evaluable patients will allow estimation of the two-sided 95% confidence interval with a width equal to 9.4% (precision 4.70%) of the PFS rate at 3 years (treated as binary variable) when the expected percentage is equal to 80%.

[Table 2](#) provides the actual width and the precision of the 95% CI and the 95% confidence limits for different percentages of PFS at 3 years when the sample size is equal to 300 of evaluable patients.

Table 2 - PFS rate at 3 yrs and corresponding 95% Confidence Intervals

PFS (%)	Actual Width (%)	Precision (%)	95% Clopper-Pearson Exact CI (%)
70%	10.7	5.35	From 64.5 to 75.1
75%	10.1	5.05	From 69.7 to 79.8
80%	9.4	4.70	From 75.0 to 84.4
85%	8.4	4.20	From 80.4 to 88.8
90%	7.1	3.55	From 86.0 to 93.2

Notes: From Gallium trial, PFS at 2 years has been estimated equal to 90% while PFS rate at 3 years to 80%.

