2.6 DETERMINATION OF SAMPLE SIZE

Sample size of this clinical study is selected based on feasibility.

Sample size is justified for the primary effectiveness endpoint POD24 treated as binary variable. A sample size of 300 evaluable patients will allow estimation of the two-sided 95% confidence interval with a width equal to 7.9% (precision 3.95%) of the POD24 when the expected percentage is equal to 13%.

The Clopper-Pearson's formula has been used for the computation.

Moreover, a sample size of 300 evaluable patients will allow estimation of the two-sided 95% confidence interval with a width equal to 9.4% (precision 4.70%) of the PFS rate at 3 years (treated as binary variable) when the expected percentage is equal to 80%.

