ⁱ FLIPI score (age, number of nodal sites, LDH level, haemoglobin, stage) or FLIPI2 (age, beta-2 microglobulin, bone marrow involvement, longest diameter of largest involved node, haemoglobin) collected at diagnosis.

^j Response will be collected at mid of the induction (between 10 and 14 weeks after the start of treatments), end of the induction (at the day of cycle 6 until 1 month later) during maintenance (1 year after the start of treatment, i.e. from 10 to 14 months after the start of treatment; 2 years after the start of treatment, i.e. from 22 to 26 months after the start of treatment; 3 years after the start of treatment, i.e. from 34 to 38 months after the start of treatment), at the end of maintenance and at Follow-up as per clinical practice, as well as at any tumor assessment that shows disease progression, CR or CRu during induction or maintenance. The assessment of tumor response will be based on standard Cheson criteria and the Deauville 5-point scale (Appendix 6) (Younes *et al.* 2017).

^k All adverse events data available in medical records after start of the treatment should be reported until 185 days after the last obinutuzumab dose or until starting a new anti-cancer therapy (whichever occurs first). After this period AEs that are believed to be related to prior study drug treatment will be collected.

Appendix 2

List of Planned Outputs

Output for baseline descriptive analyses

- Summary of demographic characteristics
- Listing of demographic characteristics
- Summary of history of treatment with Obinutuzumab and chemotherapy
- Summary of follicular lymphoma characteristics
- Summary of clinical staging pre treatment
- Summary of FLIPI/FLIPI2 (at treatment start)
- Summary of medical history (other than FL)
- Listing of medical history (other than FL)
- Summary of physical examination
- Listing of physical examination abnormalities
- Summary of vital signs and ECOG
- Listing of vital signs and ECOG
- Summary of hematology, blood chemistry and serology
- Summary of tumor assessment and target and not target lesions
- Listing of target and not target lesions
- Summary of bone marrow evaluation

Output for effectiveness analyses

- Results regarding POD24
- Results regarding PFS
- Results regarding TTNT
- Results regarding OS
- Results regarding TTLCB
- Results regarding ORR
- Results regarding CR
- Results regarding CR30
- Results regarding duration of response
- Results regarding time to response
- Results regarding SD

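### Backward selection at P > 0.05 from at least nine candidates has about a one-in-three chance of keeping a false POD24 factor, and overstates the real factors it keeps

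*SAP*

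**What the plan says.** SAP 3.2.1 uses logistic regression to find which variables predict POD24: "logistic regression analysis will be performed with backwards selection", with factors removed when P exceeds 0.05, plus univariable chi-square tests. Protocol 6.7.1 has the same rule.

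SAP 3.2.1 names no candidates. The only list is in SAP 3.2, for logistic regression on endpoint rates in general. It covers sex, age, performance status, stage, hepatitis history and FLIPI, and ends with "chemotherapy backbone choice, medical history and history of FL, comorbidities". That makes nine items, and the last two are open-ended.

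SAP Appendix 1, note i, defines the index as "FLIPI score (age, number of nodal sites, LDH level, haemoglobin, stage) or FLIPI2". FLIPI is therefore listed beside two of its own components, age and stage. FLIPI2, as defined there, contains age but not stage.

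Protocol 6.7.1 promises that the SAP will detail and justify the covariates of the multivariable models. The SAP omits that sentence and gives neither justification nor coding. It also plans no sensitivity analyses (3.4) and no handling of missing values (3.6).

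**The concern.** Backward elimination uses the same data to choose the factors and to estimate their effects. A factor survives only if its estimate is large relative to its standard error, so with few events the survivors are disproportionately those whose estimates came out too large by chance. Each null candidate also gets roughly a 5% chance of surviving, and real but moderate factors are often dropped. The intervals printed for the final model take no account of this.

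At stake is the list of factors labelled predictive of POD24, with their odds ratios. Readers may use such a list to describe who relapses early on this treatment. The rule also sits badly with two statements in the SAP: that there are no formal hypothesis tests (section 3), and that 95% intervals will accompany all estimates (3.2). A factor removed by P value has no estimate in the final model.

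**Working it through.** **The plan's own figure.** The SAP sizes the study for precision: "A sample size of 300 evaluable patients will allow estimation of the two-sided 95% confidence interval", with the width given for the case "of the POD24 when the expected percentage is equal to 13"%. It adds: "The Clopper-Pearson's formula has been used for the computation". For 39/300 the exact limits are 9.41% and 17.34%, width 7.93 and half-width 3.97. The plan states 9.4 to 17.3, 7.9 and 3.95, so the figure reproduces to rounding. Neither document gives a size, event count or power for the regression.

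**Events available.** Protocol 6.7.5 tabulates intervals "for different percentages of POD24 when the sample size is equal to 300 evaluable patients", from 11% to 17%.

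| POD24 | Events of 300 | Events per factor (9 factors) |
|---|---|---|
| 11% | 33 | 3.7 |
| 13% | 39 | 4.3 |
| 17% | 51 | 5.7 |

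If the open-ended items bring the model to 15 or 20 parameters, 39 events give 39/15 = 2.6 or 39/20 = 1.95 each. At 13%, 39 is probably an upper figure. Protocol 6.1.3 says "Approximately 300 patients will take part in this study", with no allowance over the evaluable target. Deaths within 24 months not due to progression are excluded, and unimputed covariates probably mean a complete-case fit.

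**Simulation set-ups.** The documents give no covariate prevalences or effect sizes, so these are assumptions.
- A: 300 patients, 13% events, 10 independent binary candidates with prevalence 20% to 50%.
- B: 300 patients, 13% events, nine factors coded as 10 parameters. High FLIPI is built from age, stage and three other items and entered beside age and stage; 2,000 runs per setting.

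**Chance of keeping at least one false factor when none is real.** For k independent tests it is 1 − 0.95^k: 37% for 9, 54% for 15 and 64% for 20.
- Set-up A gave 34% to 38% across runs.
- Set-up B gave 30% to 32%, rising to 45% with 15 parameters and 56% with 20.
- More events do not lower it. In A it was 35%, 38% and 38% at event rates of 10%, 13% and 17%, and 38% with 700 patients.

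**Real factors: how often kept, and how reported.** Set-up B, true effect on FLIPI:

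| True OR | Kept | Reported OR when kept | Ratio |
|---|---|---|---|
| 1.5 | 22% | 2.48 | 1.65 |
| 2.0 | about 49% | 2.76 | 1.38 |
| 2.5 | 75% | 3.06 | 1.22 |
| 3.0 | 87% | 3.45 | 1.15 |

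Set-up A agrees: a true 1.5 was kept in 20% and reported as 2.4 to 2.5, and a true 2.0 was reported as about 2.7. In B with 692 patients (692 × 0.13 ≈ 90 events), a true 2.0 was reported as 2.17 when kept, but false retention stayed at 33% to 35%.

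**Interval coverage after selection (A).** It was 82% to 88% for a true OR of 1.5 and 95% to 97% for 2 to 3.

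**The same model without selection (A).** Median ORs were 1.51, 2.04, 2.60 and 3.12 for true values of 1.5, 2, 2.5 and 3, with 94% to 95% coverage.

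**FLIPI beside its components (B).** Variance inflation factors were 1.2 to 1.4. Adding age and stage moved false retention from 24% to 32% (true FLIPI OR 2) or from 27% to 30% (no real factor), mainly because there were two more candidates. With a true FLIPI OR of 2, FLIPI was dropped while age or stage stayed in about 5% of runs.

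**The case against.** The strongest defence is that both documents call the study exploratory, with no formal tests and no multiplicity adjustment, and that the only POD24 quantity the sample size supports is the proportion with its interval. That stands, and it limits the consequence. It does not justify removing factors by P value, because an exploratory aim is better served by showing every estimate.

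It is also fair that SAP 3.2.1 names no candidates. Reading the list in SAP 3.2 as the candidate set is an inference, though no other list exists.

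A reader might infer more than the documents and calculations support:
- *That false predictors will be retained.* With nine or ten parameters, about two studies in three would keep none.
- *That the low event count causes the false retention.* It depends on the threshold and the number of candidates. Few events cause the missed factors and the exaggeration.
- *That FLIPI overlap makes the selection arbitrary.* Under the assumed correlations the effect is small, and FLIPI2 as defined does not include stage. The main problem is an unclear meaning of the FLIPI coefficient.
- *That all post-selection intervals are too narrow.* Under-coverage appeared only at a true OR of 1.5.
- *That penalisation or a cap of four or five parameters is required.* The unselected ten-candidate model was nearly unbiased, and a cap would drop covariates the protocol names.

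**Conclusion.** The point holds for the selection rule. With at least nine candidates and about 39 expected events, backward elimination at 0.05 has roughly a one-in-three chance of keeping at least one false factor, and more if the open-ended items expand. It loses a true OR of 2 in about half of studies. It overstates retained effects by about 15% (true OR 3.0) to 65% (true OR 1.5), with under-coverage for weak effects.

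These sizes rest on assumed prevalences, true odds ratios and correlations, and on the SAP 3.2 list being the candidate set. The missing covariate list and coding are a separate matter of fact: the protocol promised them and the SAP does not supply them. This should be corrected, but it does not threaten the primary POD24 estimate.

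**What to change.** In SAP 3.2.1 and protocol 6.7.1:
- Replace backward selection with one pre-specified multivariable logistic model for POD24.
- List and justify its covariates and their coding in the SAP, as protocol 6.7.1 promised. This includes how the chemotherapy backbone is grouped and which history and comorbidity variables enter.
- Enter FLIPI alone or as its components, not beside age and stage, and say whether FLIPI or FLIPI2 is used.
- Report every odds ratio with its 95% confidence interval, remove nothing by P value, and label the results hypothesis-generating. Keep the univariable table as descriptive.

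Penalised estimation, such as Firth's, is optional if the coded parameters are many or sparse. In set-up B with 20 parameters, the unselected model gave a median OR of 2.20 for a true 2.0.

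No new data are needed. Changing the SAP alone would put it in conflict with the protocol, so both must change, and protocol section 3 requires approval for changes that are not purely logistical or administrative. The downside is that there is no short list of selected factors, and intervals are wider for some covariates.

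### With chi-square as the only univariable method for POD24, age must be grouped at unstated cut-points, order is ignored and no effect size is reported

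*SAP*

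**What the plan says.** SAP 3.2.1 deals with predictors of POD24 in three consecutive sentences. The first gives the task to logistic regression. The second adds the selection method: "To identify factors associated with POD24, logistic regression analysis will be performed with backwards selection", with removal at P above 0.05. The third covers single factors: "Univariable associations between factors and POD24 will be calculated by using the Chi-square test". Protocol 6.7.1 has the same three sentences under its primary endpoint.

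The candidate factors are in SAP 3.2, where logistic regression is planned "in order to test the impact of covariates, i.e. age, sex, ECOG PS, Ann Arbor staging, FLIPI, hepatitis infection", followed by chemotherapy backbone, medical and lymphoma history, and comorbidities. Protocol 6.7.1 leaves the final covariate list and its justification to the SAP, but SAP 3.2 only repeats the general list. Neither document says how age would be grouped or how many ECOG PS or stage levels would be kept. FLIPI appears in SAP 2.4.1 and 2.5 as intermediate/high.

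SAP 3.2 also states: "Corresponding 95% confidence intervals (CIs) will be provided for all statistical estimates". SAP 3 describes the study as exploratory and SAP 3.4 plans no sensitivity analyses.

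**The concern.** A contingency-table chi-square needs categories. Age is continuous, so someone must choose a cut, and with none fixed in advance it can be chosen after the data are seen. For ordered factors with three or more levels, the test spreads its power over every pattern of differences and not only a steady rise or fall. It yields a P value alone, so the univariable column of a results table could not be compared with the odds ratios beside it.

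About 39 events are expected, so information on predictors is scarce. What is at stake is a univariable table that more easily shows no association for age, or for a multi-level ordered factor, where one exists.

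**Working it through.** **Inputs.** From SAP 2.6: "A sample size of 300 evaluable patients will allow estimation" of the interval "of the POD24 when the expected percentage is equal to 13"%, so 300 × 0.13 = 39 events. The documents give no effect size for any factor and no significance level for the univariable tests. Assumed: two-sided 5%; age approximately normal with a log-linear effect, odds ratio (OR) 1.2 to 2.0 per SD; OR 1.3 to 2.5 per step for ordered factors.

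**1. The plan's own figure.** Clopper-Pearson for 39/300 gives 9.41% to 17.34%, width 7.93%. This matches the stated 7.9%.

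**2. Age, by simulation.** Model: logit P(POD24) = a + b·x, with x standard normal, b = ln(OR) and a set so that the mean rate is 13%; 4,000 runs per OR.

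- Continuous age: score statistic U²/V, with U = Σ(x − x̄)(y − ȳ) and V = ȳ(1 − ȳ)Σ(x − x̄)², compared with 3.84.
- Grouped age: Pearson X² = Σ(O_k − n_k·ȳ)² / [n_k·ȳ(1 − ȳ)], uncorrected, on k − 1 degrees of freedom (df).

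| OR per SD | Continuous | Median split | Loss (points) |
|---|---|---|---|
| 1.0 | 4.4% | 4.8% | none (type I error) |
| 1.2 | 17.4% | 12.4% | 5 |
| 1.3 | 33.0% | 23.1% | 10 |
| 1.4 | 49.8% | 34.1% | 16 |
| 1.5 | 63.4% | 45.1% | 18 |
| 1.6 | 76.6% | 56.6% | 20 |
| 1.8 | 91.2% | 73.9% | 17 |
| 2.0 | 96.6% | 85.4% | 11 |

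Monte Carlo standard error is at most √(0.25/4000) = 0.8 points per power figure. More groups do not rescue the test: at OR 1.5 the loss is 22 points with tertiles and 23 with quartiles. A repeat with 6,000 runs at OR 1.5 gave 57% vs 40% when POD24 is 11%, and 74% vs 54% when it is 17%.

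**3. Age, by formula.** A median split of a normal variable keeps 2/π = 0.637 of the information. At 80% power the non-centrality is 7.85; 7.85 × 0.637 = 5.00, and Φ(√5.00 − 1.96) = Φ(0.28) = 0.61, a loss of 19 points. At 90% power, 10.51 × 0.637 = 6.69 gives 0.73, a loss of 17. Both agree with the simulation.

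**4. Ordered factors.** With two levels, the trend test and the uncorrected chi-square are the same test, so nothing is lost. With more levels, the trend test has 1 df and chi-square has k − 1. If order carries the whole effect, the non-centrality is the same for both:

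| Levels | Chi-square power when trend has 80% | Loss | When trend has 90% | Loss |
|---|---|---|---|---|
| 2 | 80% | 0 | 90% | 0 |
| 3 | 70.9% | 9 | 83.5% | 7 |
| 4 | 64.5% | 16 | 78.4% | 12 |
| 5 | 59.5% | 20 | 74.0% | 16 |

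Unequal levels change this. Simulation over OR 1.3 to 2.5 per step (20,000 runs each) gives a loss of 1 to 9 points for an assumed four-level 60/30/8/2% ECOG split. For an assumed 5/10/30/55% four-level factor it is 12 to 29.

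**5. Sparse cells.** A level holding an assumed 2% of patients has 300 × 0.02 = 6 patients and 6 × 0.13 = 0.78 expected events, too few for the chi-square approximation. No exact alternative is named.

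**The case against.** The best defence is that the chi-square test carries little weight here. Logistic regression is the stated route to identifying factors, age is among its covariates, and nothing makes the chi-square result a condition of entry. The sample size rests on feasibility and interval width, and SAP 3 disclaims formal hypothesis tests, so no promised power is lost. All of this stands, and it limits the point to the univariable table. It does not explain why that table should use a method that needs unspecified grouping and returns no effect size.

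A second defence is that the phrase could mean the likelihood-ratio or Wald chi-square of a univariable logistic model, which needs no grouping. The text does not settle this. If that is intended, the rewrite only makes it explicit.

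A reader might also infer more than the documents support:

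- *A loss near 20 points for every factor.* FLIPI as listed has two levels and loses nothing. Stage loses nothing if only III and IV are present, as the protocol background's use of advanced disease suggests. The ECOG loss depends on levels that are not stated.
- *A real age effect going unreported.* The multivariable model can still show it.
- *A breach of the confidence-interval promise in SAP 3.2.* A P value is not an estimate, so there is no contradiction, only a missing effect size.
- *A further loss from a continuity correction.* The documents do not say one would be applied, so it is not counted.

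**Conclusion.** The point holds as a modest, inexpensive improvement. As written, the univariable method leaves the grouping of age open, discards order where a factor has three or more levels, and gives no effect size.

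For age split at the median, with 300 patients and POD24 of 13%, the cost is about 5 to 20 points of power over OR 1.2 to 2.0 per SD, largest near 1.6. That rests on the ordinary contingency-table reading, roughly normal age, a log-linear effect and a 5% two-sided level; the effect sizes are assumptions. For ordered factors the loss runs from zero at two levels to an amount that depends on how many levels are kept and how patients spread over them.

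The POD24 proportion, its interval and the multivariable logistic model are unaffected.

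**What to change.** In SAP 3.2.1 and Protocol 6.7.1, replace the chi-square sentence with text along these lines:

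> Each factor's univariable association with POD24 will be estimated by logistic regression, reporting the odds ratio, 95% CI and likelihood-ratio P value. Age will be entered as a continuous variable, with a check of linearity. Ordered factors with three or more levels will be entered as a trend score, with the frequency table shown alongside. Unordered categorical factors will be tested by chi-square, or by Fisher's exact test where the table is sparse.

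State in the same place which levels of ECOG PS and stage are kept.

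The cost is one sentence per document plus that coding statement. It needs no new data, and R is already the named software. The real downside is the linearity (equal-step) assumption, which about 39 events can check only weakly. Showing the frequency tables lets readers see where it looks doubtful.
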